- Patients have tumor(s) amenable to biopsy.
- Under Amendments 07 and beyond, patients in F must have a known EGFR mutation and ALK translocation status.
 - Patients in F-1 must be EGFR wild type and without ALK translocation.
 - Patients in F-2 and F-3 may have an EGFR sensitizing mutation to EGFR tyrosine kinase inhibitor (TKI) therapy or ALK translocation and participate in this study if they have documented progression of their NSCLC on the appropriate tyrosine kinase inhibitor (only erlotinib, gefitinib, or afatinib, or crizotinib, respectively) and have documented progression of their NSCLC on platinum doublet chemotherapy. There is no preferred order of treatment with TKI or platinum doublet therapy, only that progression has been documented on both treatments. If a patient for F-2 or F-3 is found to have one molecular alteration (either sensitizing EGFR mutation or ALK translocation), then testing for the other alteration is not required.
 - For patients in F-1, F-2, or F-3, if a patient is known to have a mutation in KRAS, then testing for an EGFR mutation or for an ALK translocation will not be required given that all of these molecular alterations are mutually exclusive in patients with non-squamous NSCLC.

- For patients enrolled in F-1, F-2, or F-3, who are known to have a tumor of predominantly squamous histology, molecular testing for EGFR mutation and ALK translocation will not be required as this is not standard of care and is not part of current diagnostic guidelines.
- Randomized patients in F-1, F-2, and F-3 must have tumors that express PD-L1 as determined by a central vendor. The exception is the 40 patients to be enrolled in F-2 whose tumors do not express PD-L1.
- Patients in F-1 must be naive to systemic treatment for NSCLC and have Stage IV disease (adjuvant therapy may not have been administered within 1 year of the relapse).
- Under Amendment 06, patients in F-2 must have experienced progression of locally advanced or metastatic NSCLC after at least two prior systemic antineoplastic regimens (adjuvant therapy will count as a regimen if administered within 1 year before the relapse).

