- Under Amendments 07 and beyond, patients in F-2 and F-3 who are PD-L1 positive must have experienced progression of locally advanced or metastatic NSCLC after at least one prior systemic antineoplastic regimen, at least one of which must have been a platinum-containing doublet (adjuvant therapy will count as a regimen if administered within 1 year before the relapse). Patients in F-2 who are PD-L1 negative must have received at least two prior lines of systemic therapy.
- For F-2 and F-3 cohorts, Investigator-determined radiographic progression of NSCLC by RECIST 1.1 on the most recent prior therapy (and on a tyrosine kinase inhibitor if the patient has a sensitizing EGFR mutation or ALK translocation) must be determined. The site's study team must have reviewed pre-trial images that are of diagnostic quality from at least 2 dates to confirm that radiographic progression has occurred per RECIST 1.1 following initiation of the prior therapy. Note, the imaging obtained during screening may be one of the dates reviewed. These pre-pembrolizumab (MK-3475) images should be submitted to the central imaging vendor for a possible retrospective analysis of this eligibility criterion. The central vendor will not be confirming eligibility prior to randomization.
- Those patients who have received prior thoracic radiation with a dose > 30 Gy must wait at least 26 weeks from the date of completion of the thoracic radiation before the first dose of pembrolizumab (MK-3475).
- Patients in Part F with a tumor at a critical anatomic location, like abutting the thecal sac or compressing a main-stem bronchus, such that an impending catastrophic event is possible, should have that tumor lesion radiated prior to treatment with pembrolizumab (MK-3475).

- Patient has an estimated life expectancy of at least 12 weeks.
- 2) Measurable disease:
- In Part A of the study, patients may have non-measurable disease.
 - In Part B, C, D, and F of the study, patients must have measurable disease as defined per irRC (Appendix 6.5):

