The randomization of the 250 2L+ patients may be stratified by PD-L1 expression level based on a preliminary cutoff point once available, mainly based on Part C data. Data based on the patients enrolled in the non-randomized portions of Part F (Amendment 06) will be pooled with Part C data, some data from Part A, and possibly data from 1L patients in Part F (Amendment 06), to determine the final cutoff point for patients with strongly positive tumors (the primary population in this cohort) using the same estimation methods as for the melanoma patients. Just like for the melanoma patients, the cutoff point is determined in isolation to the 250 patients enrolled in the randomized portion of Part F (Amendments 07 and 08) to ensure that the subgroup analysis of the patients with strongly positive tumors is blinded to the determination process. Notice that the cutoff point is driven by patients on the Q3W schedule. To properly compare the difference (if any) in cutoff point between the two dose schedules, patients treated at 10 mg/kg Q2W will be divided into two sets with half in the training set and half in the validation set for estimation and validation of a cutoff point specifically for the Q2W schedule.

Enrollment of patients with weakly positive tumors will be capped at 50%. Besides, an interim analysis will be conducted to potentially exclude patients with weakly positive tumors (based on final cutoff point) from further enrollment (see Section 3.5.9 for details). Regardless, the final cutoff point, once determined, won't be changed for the primary analysis purposes to maintain the integrity of the analysis.

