3.5.6 Multiplicity

A Hochberg procedure will be applied to final analysis of RR and DCR for internal decision purposes based on the ipilimumab-naïve patients treated at 10 mg/kg in Part B enrolled through Amendment 4. The overall type I error rate is set at 5% (one-sided),

i.e., the trial is considered to have reached the efficacy objective if the two corresponding p-values for testing the null hypothesis (RR=10% and DCR=30%) are less than 5% OR either one is less than 2.5%. There are two planned interim analyses for administrative purposes. There is no intention to terminate the study early for efficacy, and no multiplicity adjustment is applied to the interim analyses.

The predictive biomarker hypothesis on concordance between tumor volume change and PD-L1 will be formally tested at a type I error rate of 2.5% (one-sided) separately for each part of the study, irrespective of the outcome from efficacy analyses. Once the null hypothesis is rejected, a step-down procedure may be applied to the testing of other biomarker hypotheses prospectively specified before the end of the study. While additional exploratory analyses will be conducted to evaluate alternative predictive biomarkers, there is no multiplicity control of such analyses and no formal conclusion can be made.

The efficacy hypothesis on anti-tumor activity of pembrolizumab (MK-3475) is tested at 5% (one-sided) for Part B ipilimumab-treated (non-randomized), at 10% (one-sided) for Part C, and at 2.5% (one-sided) for all other populations. Between-dose comparisons are all conducted at 20% (two-sided), or equivalent 10% (one-sided) for sample size and power calculation purpose below, except for Part B (10 mg/kg Q3W vs 10 mg/kg Q2W) which is conducted at 5% (two-sided).

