If Part F data show no evidence that line of therapy (1L vs 2L+) impacts efficacy, data will be combined across line of therapy and within dose for more powerful assessment of difference in RR between the two dose schedules and for more precise estimation of RR at a dose schedule. The pooled analysis will be conducted in the overall biomarker positive population as well as in the strongly biomarker positive population, as appropriate.

PD-L1 biomarker effect

Kendall's tau statistic will be used for testing the PD-L1 biomarker effect for various tumor and treatment groups. All testing will be conducted at type I error rate of 2.5% (one-sided). For a sample size of approximately 45 patients with both post-treatment disease assessments and valid evaluation of baseline PD-L1 expression levels in newly obtained tumor biopsies, the study has approximately 90% power to detect a one-fold

difference in concordance (i.e., odds of concordance relative to discordance = 2, or in other words tumor is twice more likely to reduce than to increase if the patient's tumor has high expression of the PD-L1 than low expression). When the sample size is reduced to 25 patients, Kendall's tau has 90% power to detect a 1.5 to 2-fold difference in concordance. In addition, the Youden index and other methods will be used for biomarker cut-off point analysis.

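### In Part F, PD-L1 negativity is tied by eligibility to heavier pretreatment, and the formal Kendall test of PD-L1 is not stratified by line of therapy

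*Combined protocol and SAP*

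**What the plan says.** Eligibility for Part F (section 2.2) sets PD-L1 status and prior treatment together. "Randomized patients in F-1, F-2, and F-3 must have tumors that express PD-L1 as determined by a central vendor"; the one exception is a group of 40 in F-2. For that group, "Patients in F-2 who are PD-L1 negative must have received at least two prior lines of systemic therapy". From Amendment 07 on, PD-L1-positive patients in F-2 and F-3 need only one prior regimen, and F-1 patients have none. Sections 1.5 and 2.4.1 put all 40 negatives on the Q2W schedule.

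The PD-L1 hypothesis, concordance between tumor volume change and PD-L1 level, "will be formally tested at a type I error rate of 2.5% (one-sided) separately for each part of the study" (section 3.5.6). Section 3.5.7 describes the unit differently: "Kendall's tau statistic will be used for testing the PD-L1 biomarker effect for various tumor and treatment groups", without defining those groups. Section 3.5.4.4 bases the analysis on evaluable patients who have a PD-L1 value and a post-treatment assessment, and does not exclude PD-L1 negatives. It separates melanoma from NSCLC, but not by line.

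No text stratifies or adjusts the Kendall test for prior lines. The one model with number of prior therapies as a covariate is in the melanoma part of section 3.5.5.4. Section 3.5.8 plans analyses of NSCLC anti-tumor activity by line and dose level, and does not mention the Kendall test.

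**The concern.** A pair made of one PD-L1-negative and one PD-L1-positive patient can compare someone with at least two prior lines against someone with none or one. If response is poorer in later lines, such pairs are concordant more often than discordant even when PD-L1 has no effect within any line. The tau statistic then drifts upward and a positive result may reflect pretreatment.

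Relating response to the degree of biomarker positivity is a stated aim of Part F (sections 1.3 and 1.4). Section 3.5.6 calls the test formal and allows other biomarker hypotheses to be tested in a step-down once it rejects. Its 2.5% error rate should therefore not depend on a baseline factor that the plan's own first-line and third-line planning rates treat as important.

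**Working it through.** **1. The plan's power figure reproduces.** Section 3.5.7 states: "For a sample size of approximately 45 patients with both post-treatment disease assessments" and PD-L1 values, "the study has approximately 90% power to detect a one-fold" difference, meaning "odds of concordance relative to discordance = 2".
- tau = (2 − 1)/(2 + 1) = 1/3.
- Null variance = 2(2n + 5)/[9n(n − 1)] = 190/17,820, so SD = 0.1033.
- Power = Φ(0.3333/0.1033 − 1.96) = Φ(1.27) = 89.8%.

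For n = 25, the SD is 0.1427. Power of 90% needs tau = 3.2416 × 0.1427 = 0.463, so odds of 2.72, a 1.72-fold difference. This lies in the stated range of 1.5 to 2. The question is therefore type I error, not the power figure.

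**2. Inputs (planned sizes, sections 1.5 and 2.4.1).**
- PD-L1 positive: 88 first-line (44 Q2W); 280 + 40 = 320 with one or more prior lines (112 Q2W); 32 with two or more (all Q3W).
- PD-L1 negative: 40, all Q2W.
- Totals: 480 in Part F; 44 + 112 + 40 = 196 on Q2W.

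Response rates in section 3.5.7:
- First line: null 25%, alternative 50%.
- 3L+: null 10%, alternative 35%.
- 2L+: 15% as historical control for strongly positive patients, 10% as the F-3 null and as the assumed Q3W rate in the between-schedule power; alternative 30%.

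**3. Model with no PD-L1 effect (assumption).** Tumor change is normal with SD 1 and mean z(RR) for the patient's line. PD-L1 is unrelated to line among positives and tied at zero in negatives. There is no schedule effect. Only positive-negative pairs then carry drift:
- d(line) = 2Φ{[z(RR line) − z(RR 3L+)]/√2} − 1
- E(S) = 40 × Σ n(line) × d(line)
- Null variance of S = [n(n − 1)(2n + 5) − 40×39×85]/18
- Rejection ≈ Φ(E(S)/SD − 1.96)

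SD for Part F: √[(480×479×965 − 132,600)/18] = 3,510. SD for Q2W: √[(196×195×397 − 132,600)/18] = 914.

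*25/10/10%:* d = 0.332 for first line and 0 for 2L+.
- Part F: E(S) = 40×88×0.3323 = 1,170; ratio 0.333; Φ(−1.63) = 5.2%.
- Q2W: 40×44×0.3323 = 585; ratio 0.640; Φ(−1.32) = 9.3%.

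*25/15/10%:* d = 0.332 and 0.138.
- Part F: 40×(29.24 + 44.03) = 2,931; ratio 0.835; Φ(−1.13) = 13.0%.
- Q2W: 40×(14.62 + 15.41) = 1,201; ratio 1.314; Φ(−0.65) = 25.9%.

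*50/30/35%:* d = 0.215 and −0.078.
- Part F: 40×(18.89 − 25.06) = −247; ratio −0.070; 2.1%.
- Q2W: 40×(9.45 − 8.77) = 27; ratio 0.029; 2.7%.

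**4. Simulation (2,000 trials per scenario, same model).** The share of 2L+ patients who have two or more prior lines is not given, so 0 and one half were both run. Cells show unstratified rejection as share 0 / share one half.

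| RR 1L/2L/3L+ | All Part F | Q2W only |
|---|---|---|
| 25/10/10% | 4.4% / 5.5% | 9.2% / 9.2% |
| 25/15/10% | 12.4% / 8.3% | 24.1% / 17.3% |
| 50/30/35% | 2.0% / 3.6% | 2.6% / 4.0% |

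With 20% in every line, run at share 0, the rates are 3.1% and 2.3%. Repeat runs at 25/15/10% spanned about 6-13% for Part F and 16-28% for Q2W. Counting pairs only within line and schedule gave about 2-3.5% throughout. The excess therefore comes from line of therapy.

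**The case against.** The strongest reply has five parts.

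- **The gradient is selective.** The 15% is a historical rate for strongly PD-L1-positive 2L+ patients, and section 3.5.7 elsewhere uses 10% for 2L+, equal to the 3L+ null. The plan's expected pembrolizumab rates, 50/30/35%, do not fall steadily with line and produce almost no inflation. This stands, and it makes 25/15/10% an upper case.
- **Everything depends on the 40 negatives entering a pooled test.** Without them, simulated rejection is 1.7-3.1% in every scenario. The only analysis stated for that cohort itself is a single-arm rule-out of a 30% response rate. Pooling across lines in section 3.5.7 is conditional on no evidence of a line effect, and is confined to biomarker-positive patients. These safeguards are real, but they govern response-rate analyses. The Kendall test has its own unit (each part) and its own analysis set, which includes negatives.
- **The test is powered at about 45 patients, not 480.** For a random 45 from Part F, error at 25/15/10% is only 4.4%. That is a planning size; no text limits the Part F test to it.
- **Schedule.** A reader might infer that putting all negatives on Q2W is a second source of bias. That needs a schedule effect on response, and section 3.1.3 reports flat dose- and exposure-response, including the F2 comparison of Q2W and Q3W.
- **Cutoff training.** A reader might also infer that the NSCLC cutoff is distorted, because the training set may include "possibly data from 1L patients in Part F (Amendment 06), to determine the final cutoff point". The inclusion is only possible, and Table 2-1 shows 6 + 5 = 11 such patients beside 41 in Part C and 33 in the Amendment 06 3L+ group. The effect was not simulated, so this is minor.

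**Conclusion.** The concern holds in a limited form. Eligibility links low PD-L1 to at least two prior lines, and the formal Part F test as written does not account for line. If response falls with line, its error exceeds 2.5%: about 5% for all Part F and 9% within Q2W at 25/10/10%, about 6-13% and 16-28% at 25/15/10%, and about 2-4% at 50/30/35%.

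A reader might take the double-digit figures as the expected error. The documents do not support that: those figures need the 15% rate applied to all 2L+ patients, and the highest also assume that no 2L+ patient has two or more prior lines.

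The result rests on the assumed gradient, the unstated mix of lines within 2L+, PD-L1 being unrelated to line among positives, and 40 negatives. Table 2-1 lists 156 negatives, but its Part F rows sum to 53 + 50 + 33 + 156 + 172 + 112 + 55 = 631 against 519 enrolled in section 1.5. The other rows leave 519 − 475 = 44, so the planned 40 was used.

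The unit of the test also matters. Read as dose or schedule groups, section 3.5.7 leaves the bias in place, and it is larger within Q2W. Read as separate line-by-schedule cohorts, the bias goes but the negatives have no PD-L1-positive comparators.

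**What to change.** In sections 3.5.5.4, 3.5.6 and 3.5.7:

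1. Define the unit of the Part F Kendall test, reconciling each study part (3.5.6) with treatment groups (3.5.7), and say whether PD-L1 negatives enter it.
2. Compute tau from pairs within strata of prior regimens (0, 1, 2 or more), summing S and its variance over strata. Stratifying by schedule as well is optional.
3. Compare the negative cohort's response rate only with PD-L1-positive patients who have at least two prior lines.
4. Minor: if Amendment 06 first-line patients enter the NSCLC cutoff training set, stratify by line or check the cutoff without them.

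Comparators exist. The Amendment 06 F-2 group has 32 planned PD-L1-positive patients with at least two prior lines, on Q3W, and the randomized F-2 arms admit others. Stratifying by schedule too would remove those 32 as comparators for the negatives and leave only Q2W positives with two or more prior lines, whose number is not stated.

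The cost is fewer usable pairs and somewhat lower power. Prior treatment and schedule already define the cohorts, so no new data should be needed. Enrollment is complete (section 1.5) and section 3.1.3 already cites F2 results, so the stratified test cannot be presented as pre-specified on unseen data. The change, its timing and its reason should be listed in the clinical study report, as the opening of section 3.5 requires.

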2.3 PATIENT EXCLUSION CRITERIA

A patient meeting any of the following criteria is not eligible to participate in this study:

- 1) Patient who has had chemotherapy, radioactive, or biological cancer therapy within 4 weeks prior to the first dose of study therapy, or who has not recovered to CTCAE grade 1 or better from the adverse events due to cancer therapeutics administered more than 4 weeks earlier. Patient who has had erlotinib, gefitinib, afatinib, or crizotinib within 1 week prior to the first dose of study therapy, or who has not recovered to CTCAE Grade 1 or better from the adverse events due to any of these drugs administered more than 1 week earlier.
 - Patient who has had ipilimumab therapy may be enrolled in Part B or Part C of the study (after 13 ipilimumab naïve patients are enrolled in Part B) if the requirements specified in Inclusion Criterion 1) are met.

- 2) Patient is currently participating or has participated in a study of an investigational agent or using an investigational device within 30 days of administration of pembrolizumab (MK-3475). Note: This does not include participation in the follow-up phase of a study.
- 3) Patient is expected to require any other form of antineoplastic therapy while on study (including maintenance therapy with another agent for NSCLC).
- 4) Patient has a medical condition that requires chronic systemic steroid therapy or requires any other form of immunosuppressive medication. However, patients using physiologic replacement doses of hydrocortisone, or its equivalent, will be considered eligible for this study: up to 20 mg hydrocortisone (or 5 mg of prednisone) in the morning and 10 mg hydrocortisone (or 2.5 mg of prednisone) in the evening.
- 5) Patient has risk factors for bowel obstruction or bowel perforation (examples include but not limited to a history of acute diverticulitis, intra-abdominal abscess, abdominal carcinomatosis).
- 6) Patient has a known history of a hematologic malignancy, malignant primary brain tumor or malignant sarcoma, or of another malignant primary solid tumor, unless the patient has undergone potentially curative therapy with no evidence of that disease for 5 years.
 - Note: The time requirement for no evidence of disease for 5 years does not apply to the tumor for which a patient is enrolled in the study. The time requirement also does not apply to patients who underwent successful definitive resection of basal cell carcinoma of the skin, superficial bladder cancer, squamous cell carcinoma of the skin, in situ cervical cancer, or other in situ cancers.
- 7) Patient has known active central nervous system (CNS) metastases and/or carcinomatous meningitis. Patients with previously treated brain metastases may participate provided they are clinically stable for at least 4 weeks prior to study entry, have no evidence of new or enlarging brain metastases and are off steroids for at least 7 days from first dose of pembrolizumab (MK-3475).
- 8) Patient previously had a severe hypersensitivity reaction to treatment with another mAb.
- 9) Patient has a history of non-infectious pneumonitis that has required a course of oral or intravenous steroids to assist with recovery, or interstitial lung disease.
- 10) Patient has an active autoimmune disease or a documented history of autoimmune disease or syndrome that requires systemic steroids or immunosuppressive agents. Patients with vitiligo or resolved childhood asthma/atopy would be exception to this rule. Patients that require inhaled steroids or local steroid injections would not be excluded from the study. Patients with hypothyroidism not from autoimmune disease that is stable on hormone replacement will not be excluded from the study.

- 11) Patient had prior treatment targeting PD-1: PD-L1 axis or CTLA (with exception of ipilimumab in study Part B and Part C), or was previously randomized in any pembrolizumab (MK-3475) trial.
 - Examples of such agents include (but are not limited to): Nivolumab (BMS-936558 MDX-1106 or ONO- 4538); Pidilizumab (CT011); AMP-224; BMS-936559 (MDX 1105); MPDL3280A (RG7446); and MEDI4736.
- 12) Patient has an active infection requiring therapy.
- 13) Patient is positive for Human Immunodeficiency Virus (HIV) (HIV 1/2 antibodies), active Hepatitis B (HBsAg reactive) or Hepatitis C (HCV RNA (qualitative) is detected); patients with negative Hepatitis C antibody testing may not need RNA testing.
- 14) Patient has a history or current evidence of any condition, therapy, or laboratory abnormality that might confound the results of the study, interfere with the patient's participation for the full duration of the study, or is not in the best interest of the patient to participate, in the opinion of the treating Investigator.
- 15) Patient has known psychiatric or substance abuse disorders that would interfere with cooperation with the requirements of the trial.
- 16) Patient is, at the time of signing informed consent, a regular user (including "recreational use") of any illicit drugs or had a recent history (within the last year) of substance abuse (including alcohol).
- 17) Patients with symptomatic ascites or pleural effusion. A patient who is clinically stable following treatment for these conditions (including therapeutic thoraco- or paracentesis) is eligible.
- 18) Patient is pregnant or breastfeeding, or expecting to conceive or father children within the projected duration of the study.

